8.2.2.2 OL-300 Analyses

Descriptive summaries will be presented overall and in each age-group, in total and by initial randomized treatment group (placebo/dose level/overall active) in the OLS-300, using different definitions of baseline values, as described in [Section 8.2.1.2](#)

1. Considering the CRD determined by screening DBPCFC as baseline CRD.
2. Considering the CRD determined by the DBPCFC which was conducted prior to the subject receiving any active treatment as baseline CRD.

The absolute CRD values at each timepoint will be presented, in addition with the change from screening and from last value prior any active treatment, taking the different types of baseline into account.

In addition the number (%) of subjects with CRD improvement / stable / deterioration from screening DBPCFC and from last DBPCFC prior any active treatment at each timepoint will be presented, using the following definitions:

- Improvement: CRD at timepoint > CRD at baseline
- Stable: CRD at timepoint = CRD at baseline
- Deterioration: CRD at timepoint > CRD at baseline

with baseline denoting screening DBPCFC or last DBPCFC prior any active treatment, respectively.

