3 STUDY OBJECTIVES

The objectives of this study are

- To evaluate the safety and efficacy of Viaskin Milk after 12 months of epicutaneous Immunotherapy (EPIT) treatment, for desensitizing Immunoglobulin E (IgE)-mediated cow's milk-allergic children.
- To assess the long-term safety and efficacy of up to 48 months of treatment with Viaskin Milk.

This document is confidential

Statistical Analysis Plan

- To assess the safety and the therapeutic benefit of the most effective tested dose of Viaskin Milk over 24 months of treatment.

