8.2.1.2 OL-300 Analyses

Optional food challenge can be performed after 12 months and/or 24 months of open-label treatment with Viaskin Milk 300 μ g. No DBPCFC was performed at the end of 500 μ g period (prior to switch to open-label treatment with Viaskin Milk 300 μ g).

A responder in the OL-300 analyses is defined as a subject who meets at least one of the following criteria:

- A \geq 10-fold increase in the cow's milk proteins CRD at the Month 12 DBPCFC (VS3/VS4) [Month 24 (VS6/VS7)] after switch to Viaskin Milk 300 μ g as compared to baseline value and reaching at least 144 mg of cow's milk proteins
- A CRD of cow's milk proteins \geq 1444 mg at the Month 12 DBPCFC (VS3/VS4) [Month 24 DBPCFC (VS6/VS7)] after switch to Viaskin Milk 300 μ g

Two types of analyses will be performed, considering different timepoints as baseline:

1. Considering the CRD determined by screening DBPCFC as baseline CRD.
2. Considering the CRD determined by the DBPCFC which was conducted prior to the subject receiving any active treatment as baseline CRD. This refers to Month 12 DBPCFC for subjects randomized to the placebo treatment arm and to screening DBPCFC for subjects randomized to any active treatment arm.

This document is confidential

Statistical Analysis Plan

Both types of responders will be summarized overall and in each age-group, in total and by initial randomized treatment group (placebo/dose level/overall active) in the OLS-300.

For the calculation of rates and percentages, only the subjects with DBPCFC at the respective baseline and at Month 12 (VS3/VS4) [Month 24 (VS6/VS7)] after switch will be used.

8.2.2 Cumulative Reactive Dose (CRD) of Cow's Milk Proteins at Months 12 to 48

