8.2.2.1 Double-blind Month 12 and OL-500 analyses

The actual value and changes from baseline of CRD of Cow's milk proteins was summarized overall and for each age group, in total and by (initial randomized) treatment group (placebo/dose level/overall active), at each time point until Month 12 on the ITT for the randomized blinded treatment period. This analysis was repeated until Month 48 (if applicable) for the Viaskin Milk 500 μ g open-label treatment period on the OLS-500 and on PPS-500. Change from Month 12 to each timepoint was also tabulated for the OL-500 period.

An ANCOVA model was built to compare the mean value in \log_{10} -transformed CRD at Month 12 between each dose level group and placebo for subjects in the ITT. Treatment group, age group, and baseline \log_{10} -transformed CRD were included in the model. The adjusted Least Squares Mean (LS-Mean) differences versus placebo were reported together with associated 95% confidence intervals and corresponding p-values. A SAS code similar to the following was be used.

```
PROC MIXED DATA =<indata>;
  CLASS agegroup treat;
  MODEL aval = base agegroup treat / DDFM=kr;
  LSMEANS treat/cl diff;
RUN;
```

In addition to the analysis of the \log_{10} -transformed data, a sensitivity analysis was performed using an appropriate non-parametric test procedure. The treatment effect was estimated using Hodges-Lehmann estimate of the difference in medians of CRD change from month 0. The corresponding 95% confidence interval and the p-value from the hypothesis test of no difference between the treatment groups (Wilcoxon rank-sum test) stratified on age group were presented.

The ANCOVA model and its sensitivity analysis will not be repeated for open-label time points.

Note that only the active milk food challenge will be included, placebo food challenges will not be included.

This document is confidential

Statistical Analysis Plan

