8.2.3.2 OL-300 Analyses

During OL-300 analyses, Cow's milk specific IgG4 were no longer collected and analyzed.

The following values will be summarized for the immunological markers using descriptive statistics overall and for each age group, visit and time point in total and by initial randomized treatment group (placebo/dose level/overall active) on the OLS-300.

- Absolute values at Month 0, Month 12, last value prior to switch to Viaskin Milk 300 μ g and all scheduled visits in the analyzed OL-300 period
- Changes from last value prior to any active treatment
- Changes from last value prior to switch to Viaskin Milk 300 μ g

Actual values for the immunological markers will be displayed graphically by treatment group in the course of time during the analyzed OL-300 period.

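### For active-arm subjects both OL-300 baselines for CRD and response are the screening challenge, so no planned change, category or responder table shows their paired change since Month 12

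*SAP*

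**What the plan says.** SAP 8.2.1.2 plans the OL-300 responder analysis in two types. Type 1 is defined by "Considering the CRD determined by screening DBPCFC as baseline CRD". Type 2 uses the last challenge before any active treatment, which it spells out as "Month 12 DBPCFC for subjects randomized to the placebo treatment arm and to screening DBPCFC for subjects randomized to any active treatment arm". SAP 8.2.2.2 carries both baselines into the CRD summaries, which give absolute values by timepoint, "in addition with the change from screening and from last value prior any active treatment". It adds a table of improvement, stable and deterioration against each.

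SAP 8.2.1.2 also notes the design constraint: "No DBPCFC was performed at the end of" the 500 µg period. Month 12 challenges were scheduled for all subjects, however, and the footnote to SAP Table 2 says that some Month 24 and Month 36 challenges had been done before Amendment 5 removed them.

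Elsewhere the SAP does use later reference points. For CRD in OL-500, section 8.2.2.1 states: "Change from Month 12 to each timepoint was also tabulated for the OL-500 period". For OL-300, the immunological markers (8.2.3.2) get "Changes from last value prior to switch to Viaskin Milk" 300 µg, and the skin prick test (8.2.4.2), FAQLQ (8.2.6.1.3) and FAIM (8.2.6.2.3) sections plan the same.

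**The concern.** The third study objective in SAP section 3 is "To assess the safety and the therapeutic benefit of the most effective tested dose of Viaskin Milk over 24 months of treatment". For active-arm subjects the responder rate and the improvement table for OL-300 measure something wider: everything since screening, including the blinded year at the randomised dose and an OL-500 period whose length varies by subject. A subject who responded at Month 12 and has since stayed level, or lost ground, can still be counted as a responder with improvement after the switch. The second type of analysis looks like a check on the first, but gives different answers only in the placebo arm. At stake is how far these tables can inform the third objective. The primary Month 12 analysis is not affected.

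**Working it through.** **Inputs**
- Challenge doses from Month 12 on: 1, 3, 10, 30, 100, 300, 1000, 2000 and 3000 mg; screening stops at 300 mg (protocol 7.3.1.1.1 and 7.3.1.1.2).
- Responder rule: at least a 10-fold rise in CRD reaching at least 144 mg, or a CRD of at least 1444 mg (SAP 4.1, 8.2.1.2).
- Randomised: 198, with 18 in Part A and 180 in Part B (SAP 3.1). Part A was 2:1 active to placebo, Part B 1:1:1:1 (SAP 3.4.1, 3.4.2.1).

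**1. The plan's own thresholds.** The cumulative doses are 1, 4, 14, 44, 144, 444, 1444, 3444 and 6444 mg. Both 144 and 1444 mg are exact steps, so the ladder reproduces the plan's figures.

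**2. Baselines by arm**

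| Initial arm | Type 1 baseline | Type 2 baseline |
|---|---|---|
| Any active dose | Screening | Screening |
| Placebo | Screening | Month 12 |

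For active arms, types 1 and 2 are the same calculation.

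**3. How many subjects.** Part A active: 18 × 2/3 = 12. Part B active, assuming an even split: 180 × 3/4 = 135. Total 12 + 135 = 147, and 147/198 = 74%. The planned numbers give the same share: (12 + 132)/194 = 144/194 = 74%.

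**4. Two illustrative active-arm subjects**

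| Screening | Month 12 | After switch | Against screening, as planned | Against Month 12 |
|---|---|---|---|---|
| 14 mg | 1444 mg | 444 mg | +430 mg; 444/14 = 31.7-fold; improvement; responder | −1000 mg; 1 − 444/1444 = 69% fall |
| 14 mg | 444 mg | 444 mg | +430 mg; 31.7-fold; improvement; responder | No change |

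**5. All ladder patterns.** There are 6 possible screening values and 9 values at each of Month 12 and the post-switch challenge, with full doses and no repeats assumed.
- Loss since Month 12: 6 × 36 = 216 patterns. Of these, 83 are above screening (improvement), 33 equal and 100 below; 42 are still responders.
- No change since Month 12: 6 × 9 = 54 patterns, of which 33 count as improvement and 25 as responder.

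These count possible patterns, not expected frequencies.

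**6. Do the general rules fill the gap?** SAP 6.1.1 makes summaries relative to Month 0 and Month 12 the default, but only where nothing else is specified, and 8.2.2.2 specifies its own baselines. SAP 6.2.1 also defines Month 12 so as to leave out assessments made during a challenge. The same section names the last OL-500 value as a baseline for OL-300 analyses, but 8.2.2.2 does not invoke it, and for CRD it exists only where a Month 24 or 36 challenge was done.

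**7. A related slip.** In 8.2.2.2, Deterioration carries the same greater-than sign as Improvement. As written, the first example subject meets both categories against screening, and against Month 12 the loss would meet none of the three.

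**The case against.** The strongest reply is that a clean pre-switch CRD baseline does not exist for most subjects, because challenges stopped while they were on 500 µg. Month 12 to the post-switch challenge still mixes OL-500 with OL-300. That stands: a Month 12 baseline removes only the blinded year, and a reader should not infer that it would isolate the effect of 300 µg. For placebo-arm subjects it is already the type 2 baseline.

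Three stronger readings are tempting, and the documents do not support them.
- *CRD and response alone lack a pre-switch comparison.* Symptom severity during the milk challenge is also an open-label efficacy endpoint (SAP 4.2.2), and 8.2.5.2 plans no pre-switch change for it. The divide is between challenge-based measures and those taken at the switch visit.
- *Later losses are hidden.* Absolute CRD at each timepoint is planned, and SAP 6.1.4 puts all relevant data in listings by subject and visit. But 8.2.2.2 does not say whether Month 12 is among the timepoints, and group values are not paired change.
- *Earlier gains are presented as the effect of 300 µg.* The CRD changes are labelled by their baseline, and the endpoint covers the course of open-label treatment at both doses. A pre-treatment baseline also suits the long-term objective. The risk is one of interpretation, helped by 8.2.1.2 naming these subjects responders in the OL-300 analyses.

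Finally, challenge stopping rules differ in the 300 µg period (protocol 7.3.1.1.3), so change from Month 12 carries that difference. So do the planned changes from screening; it calls for a footnote.

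**Conclusion.** The point holds in a limited form. For active-arm subjects the two baselines are identical, and every planned OL-300 change, category and responder summary for them is cumulative from screening. None shows paired change since Month 12 or the last pre-switch challenge, although the SAP did this for CRD in OL-500 and uses the last pre-switch value for immunology, skin prick test and quality of life.

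The 74% is a share of randomised subjects and rests on an even Part B split. It should not be read as the share of the analysed set, which is OLS-300 subjects with an optional challenge and the respective baseline challenge; the split there is not given. The examples show what the rules permit, not how often it happens. These are descriptive secondary analyses, so this is a worthwhile, inexpensive improvement that brings them closer to the third objective.

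**What to change.** 1. In SAP 8.2.2.2, add paired CRD change and improvement/stable/deterioration from the Month 12 challenge, for all arms, at VS3/VS4 and VS6/VS7. Where a Month 24 or 36 challenge exists, show change from the latest one separately; pooling would mix baselines of different age.
2. Correct Deterioration to a post-switch CRD less than the baseline CRD. This is needed whatever the baseline.
3. In SAP 8.2.1.2, cross-tabulate responder status at Month 12 by status at VS3/VS4 and at VS6/VS7, by initial arm. A new baseline alone would not be enough, because the 1444 mg criterion does not depend on baseline.
4. Label the type 1 and type 2 results as cumulative response to all active treatment to date. State that change from Month 12 still includes an OL-500 period of variable length, is limited to subjects taking the optional challenge, and spans a change in stopping rules.

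The cost is SAP wording and a few extra descriptive tables. The data are already in the collection plan and no further challenge is needed. The apparent OL-300 benefit may look smaller.

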All DBPCFCs at Month 12 and forward will be conducted using the same procedures that are described for the screening DBPCFC, with the exception that the dosing will continue beyond the 300 mg dose of cow's milk proteins if there are no objective symptoms (see [Section 7.3.1.1.3](#)) at the 300 mg dose. The challenge must be continued up to the last dose of 3000 mg of cow's milk proteins or until an objective reaction occurs (as defined in [Section 7.3.1.1.3](#)).

For all DBPCFCs at Month 12 and forward, the doses of cow's milk proteins will be 1 mg, 3 mg, 10 mg, 30 mg, 100 mg, 300 mg, 1000 mg, 2000 mg, and 3000 mg administered at 20-minute intervals. The Investigator may use clinical judgment to increase the intervals between doses in case there is a suspicion that an objective reaction may be developing (see [Section 7.3.1.1.3](#)). Very occasionally, the Investigator may use clinical judgment to repeat the same dose (only once) before administration of the next higher dose and only if there is a suspicion that an objective reaction may be developing (see [Section 7.3.1.1.3](#)). The dose and time of administration of each dose (and of a repeated dose when applicable) will be recorded in the eCRF. The subjects

will be kept under observation for an additional 3 hours after the ingestion of the last dose of the challenge formula.

Subjects should undergo both days of the DBPCFC (milk and placebo). However, in exceptional cases, the DBPCFC on the second day of the challenge might not be performed if the subject had a severe anaphylactic reaction during the first day of the challenge, leaving no doubt about the nature of the formula administered, ie, cow's milk. In this rare case and in this case only, the formula will be unblinded to confirm that the subject effectively received the milk formula. A severe anaphylactic reaction would involve a >20% drop of blood pressure, cyanosis or SpO₂<92%, confusion, collapse, loss of consciousness, 3 doses of epinephrine or more (see [Appendix 14.4](#)).

At the end of the second day of the food challenge, the sequence of the 2 formulas (milk or placebo) administered will be unblinded by the appropriate unblinded staff (eg, dieticians, study nurses, pharmacists, pharmacy technicians, licensed medical assistants, or any other qualified site personnel, as delegated by the Investigator) and revealed to the medical staff. The results of the challenge will then be established and recorded in the eCRF.

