7.3.1.1.3 Criteria for Stopping the DBPCFC

The instructions for each of the DBPCFCs during the double-blind period (Screening, Month 12), the Viaskin Milk 500 µg open-label period (Month 24, Month 36 and Month 48) and the Viaskin Milk 300 µg open-label period (12 and 24 months after the switch) are provided below. Further details are provided in the Manual of Procedures for the DBPCFC.

Only clear-cut OBJECTIVE immediate-type symptom(s) requiring treatment will be considered a permissible reason to stop the DBPCFC and to determine the eliciting dose (highest dose given during the challenge) and the CRD of cow's milk. For the open-label treatment period with Viaskin Milk 300 µg, abdominal complaints will also be considered as a criterion for stopping the challenge (see below). The main objective symptoms to expect are as follows (this list is not exhaustive; also refer to [Appendix 14.2](#), OFC Symptom Score Sheets^{21, 22}): local or generalized pruritus, flushing, local or generalized urticaria, hives, swollen lips, swollen tongue, throat tightness, vomiting, diarrhea, dyspnea, rhinorrhea, sneezing, wheezing, conjunctivitis, asthma, drop of the PEF, hypoxia, hypotension, hypotonia, decreased level of consciousness associated with collapse and/or incontinence or other life threatening symptoms.

The stopping rules applying for DBPCFCs performed during the double-blind placebo-controlled period and the open-label treatment period with Viaskin Milk 500 µg were the following:

- There is a >1-point rise in an objective symptom from any category in the OFC Symptom Score Sheets, except only for pruritus, which requires >2-point rise
- There is ≥1-point rise in an objective symptom from ≥2 categories in the OFC Symptom Score Sheets
- There is a 1-point rise in an objective symptom from 1 category in the OFC Symptom Score Sheets, with the following exceptions:
 - Pruritus : 0 to 1 or 0 to 2
 - Urticaria: 0 to 1

- Rash: 0 to 1
- Sneezing/Itching: 0 to 1
- Nasal Congestion: 0 to 1
- Rhinorrhea: 0 to 1
- Laryngeal: 0 to 1 (if explained and not persistent)

The stopping rules applying for DBPCFCs performed during the open-label treatment period with Viaskin Milk 300 µg are the following:

Only 1 out of 5 categories has increased its grading symptom score

≥ 1-point rise (i.e. mild, moderate or severe)	OR	≥ 2-point rise (i.e. moderate or severe)	OR	3-point rise (i.e. severe)

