4 ENDPOINTS

4.1 PRIMARY EFFICACY ENDPOINT

The primary efficacy endpoint was the percentage (%) of subjects who were treatment responders after the first 12 months of EPIT treatment.

A treatment responder is defined as a subject who meets at least one of the following criteria:

- A \geq 10-fold increase in the Cumulative Reactive Dose (CRD) of cow's milk proteins at the Month 12 DBPCFC as compared to baseline value and reaching at least 144 mg of cow's milk protein (approximately 4.5 mL of milk)
- A CRD of cow's milk proteins \geq 1444 mg (approximately 45 mL of milk) at the Month 12 DBPCFC.

The cumulative reactive dose (CRD) of cow's milk proteins is entered directly in CRF by the sites and is calculated as the sum up of all doses of cow's milk proteins given during the challenge, including repeat doses if applicable, and exact quantity of the last dose given (if not given in totality).

This document is confidential

Statistical Analysis Plan

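### The OL-300 CRD classes call a subject stable only if two CRDs are equal, yet the CRD varies with repeat and part-eaten doses at the same eliciting dose

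*SAP*

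**What the plan says.** SAP 8.2.2.2 summarises the CRD in the OLS-300 against two baselines: the screening challenge, and the last challenge before any active treatment. After absolute values and changes it adds counts and percentages in three classes:

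- "Improvement: CRD at timepoint > CRD at baseline"
- "Stable: CRD at timepoint = CRD at baseline"
- "Deterioration: CRD at timepoint > CRD at baseline"

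There is no tolerance and no grouping by dose step.

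Under SAP 4.1 the CRD "is entered directly in CRF by the sites and is calculated as the sum up of all doses" of milk protein given, "including repeat doses if applicable, and exact quantity of the last dose given (if not given in totality"). Protocol 8.1.6.1 has the same definition. Protocol 7.3.1.1.1 and 7.3.1.1.2 let the investigator, rarely, give a dose a second time (once only) when an objective reaction is suspected.

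Two further provisions matter. Protocol 7.3.1.1.3 treats the eliciting dose as a quantity separate from the CRD; the stopping symptoms serve "to determine the eliciting dose (highest dose given during the challenge) and the CRD". And for challenges from Month 12 onward, Protocol 7.3.1.1.2 states: "The dose and time of administration of each dose (and of a repeated dose when applicable) will be recorded in the eCRF". Section 7.3.1.1.1 has the matching provision for screening.

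**The concern.** The classes are meant to show whether a child's reaction threshold rose, held or fell. At a fixed eliciting dose, however, the CRD also depends on how the challenge went: whether a dose was repeated, and how much of the last cup was eaten. An equality rule turns any such difference into a change of class, although the child reacted at the same step both times.

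The third line makes this worse. Because it carries the same sign as the first, a higher CRD meets two classes and a lower CRD meets none. Correcting the sign is necessary but leaves the scale problem in place.

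The OL-300 period has no concurrent control, its challenges are optional, and SAP 8.2.2.1 does not repeat the CRD model for open-label time points. The class table is therefore one of the few planned views of gain or loss at this dose.

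**Working it through.** **Inputs.** Dose ladders from Protocol 7.3.1.1.1 (1, 3, 10, 30, 100, 300 mg at screening) and 7.3.1.1.2 (the same, then 1000, 2000, 3000 mg). CRD definition from SAP 4.1. Class rules from SAP 8.2.2.2. Responder cut-offs of 144 and 1444 mg from SAP 4.1 and 8.2.1.2.

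**1. Reproduce the plan's figures.** The running sums of the ladder, with no repeat and every dose eaten in full, are 1, 4, 14, 44, 144, 444, 1444, 3444 and 6444 mg. So 144 = 1+3+10+30+100 and 1444 = 144+300+1000. Both cut-offs are exact no-repeat ladder sums.

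**2. Spread of CRD at one eliciting dose.**

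| Challenge | Ends at 100 mg | Ends at 300 mg |
|---|---|---|
| No repeat, all eaten | 144 | 444 |
| 1 mg repeated | 145 | 445 |
| 10 mg repeated | 154 | 454 |
| Last dose repeated | 244 | 744 |
| Half of last dose eaten | 44+50 = 94 | 144+150 = 294 |

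**3. Apply the class rules at 300 mg.**

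- 444 to 444: *stable*.
- 444 to 454 or 744: *improvement*, and as printed also *deterioration*.
- 444 to 294, or 744 to 444: *deterioration* if less-than was meant; no class as printed.

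The same pattern appears at every screening step. Order can even reverse: 744 mg (300 mg repeated) exceeds 644 mg (444 plus 200 mg eaten of the 1000 mg dose), so a child who went a step further would have the lower CRD.

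**4. How often.** The documents give no rate of repeats or part doses. Let q be the assumed probability that a challenge has one, independent between the two challenges, and ignore identical deviations. The share of true same-dose pairs that miss *stable* is 1 − (1 − q)²:

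| q | Share missing *stable* |
|---|---|
| 2% | 4% |
| 5% | 10% |
| 10% | 19% |
| 20% | 36% |

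**5. Margin at the responder cut-offs.** The lowest qualifying CRD is min(max(10 × baseline, 144), 1444). Compare it with the first ladder sum that reaches it:

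| Baseline CRD (mg) | Bar (mg) | Ladder sum (mg) | Margin (mg) |
|---|---|---|---|
| 1, 4 or 14 | 144 | 144 | 0 |
| 44 | 440 | 444 | 4 |
| 144 | 1440 | 1444 | 4 |
| 444 | 1444 | 1444 | 0 |

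An entered 143 in place of 144 would change status where the margin is 0. A 1 mg repeat at baseline also moves the bar: 15 × 10 = 150 exceeds 144, and 45 × 10 = 450 exceeds 444.

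**The case against.** The strongest reply is that this is a small matter in a supplementary table. The classes come on top of absolute CRD and change, nothing is tested, responder rates have their own rules, and repeats are meant to be rare. All of that stands and limits the size of the point. A repeat also does not always break equality, since identical repeats at both challenges cancel. Nor can repeats at follow-up carry a subject over a fixed cut-off a step early: with every dose repeated, the CRD is at most 2 × 44 = 88 mg before the 100 mg dose and 2 × 444 = 888 mg before the 1000 mg dose.

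The eliciting step is not perfect either. It ignores that a child may tolerate a dose once and react only to its repeat. Read as the highest dose given, it credits a child who ate a little of the next dose. It does not separate a reactor from a non-reactor at 3000 mg. It also cannot remove the difference between the OL-300 stopping rules and those used at screening and Month 12 (Protocol 7.3.1.1.3). These are reasons to state the step rule carefully and to keep the CRD classes beside it.

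A reader might infer that responder status hangs on totals added by hand by unblinded staff. The documents do not support this. SAP 4.1 says only that sites enter the sum. Protocol 9.3 plans automated consistency checks and queries, and the data validation specification is not among the documents, so a CRD check may exist. Treatment was blinded up to Month 12 (Protocol 6.4), and at every challenge the assessors do not know the formula order until the end of the second day (Protocol 7.3.1.1 and 8.4).

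**Conclusion.** The point holds for the OL-300 class table and should be corrected. Exact equality is applied to a quantity that varies within one eliciting dose, and the documents do not adjust the CRD before it is classified. At 100 mg, same-dose challenges span 94 to 244 mg in the cases shown. How many subjects this affects is unknown; the 4% to 36% range rests entirely on the assumed 2% to 20% per challenge and on independence. The misprinted deterioration sign is certain and needs no assumption.

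The 0 or 4 mg responder margins justify a programmed check of the CRD. They do not show that any entered value is wrong. Nor do they call for reopening the Month 12 primary result, which SAP 11.1 records as analysed, unblinded and reported.

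**What to change.** 1. In SAP 8.2.2.2, define the classes by eliciting dose step: *improvement* is a higher step than at the baseline challenge, *stable* the same step, *deterioration* a lower step. State how a part-eaten last dose counts, and where a subject without a reaction at 3000 mg belongs.
2. Keep the CRD-based classes as a companion display, with the deterioration sign changed to less-than.
3. Before the Year 2 analysis, recompute each CRD by program from the dose-level eCRF records, compare it with the site-entered total, and query any difference.
4. Leave SAP 4.1 and the reported Month 12 primary endpoint unchanged. Screening and Month 12 CRDs serve as OL-300 baselines, so disclose any that come to differ from the 12-month CSR.

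The cost is a little programming, some queries and a second small table. No new data are needed.
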